6. TREATMENT

6.1 Treatment Administration

6.1.1. Sunitinib

Sunitinib will be provided by the Trial Sponsor. Sunitinib will be administered at a dose of 37.5 mg per day (1 capsule of 25 mg and 1 capsule of 12.5 mg) orally for 28 days on an ongoing basis. It must always be taken at the same time every day (or as close as possible) and capsules must be swallowed whole. Food does not appear to affect the bioavailability of the drug. A 37.5 mg dose was chosen based on the approved dose of sunitinib for the treatment of pancreatic neuroendocrine tumours (pNET). If the patient requires a sunitinib dose reduction, the dose adjustment stated in section 6.3 will be followed.

On days when TH-302 is also administered, sunitinib must be taken 2 hours before, or at least 2 hours after TH-302 infusion. Given its hypoxia-inducing ability in highly vascular tumour tissue and its TH-302-enhancing effect, sunitinib will be administered as monotherapy in the first week of treatment.

If, for any reason, the patient skips a dose or vomits after ingestion, a double dose should not be taken the following day. Treatment will resume on the following day with the usual daily dose. In contrast, if for any reason an additional dose is taken, the following day's dose should be skipped.

The study drug will be supplied in 25 mg and 12.5 mg capsules. The study drug must be handled and stored safely and as specified on the label. The label on the bottles will indicate the study protocol number, the medication or bottle number, the contents, instructions for use, storage instructions, the clinical trial declaration and the name of the sponsor. The patient number will be allocated to a bottle upon hand over.

Patients will be instructed as to its correct administration and that it must be kept at room temperature (15-25 °C) and out of the reach of children. Site staff must ensure that the patient understands the instructions for correct outpatient use of the drug.

Patients will receive enough medication until the next visit, and must return the containers with any surplus medication for it to be accounted for. This will take place on day 1 of each cycle prior to dispensation of medication for the next cycle. Any surplus medication returned by the patient for it to be accounted for will not be dispensed again, and the number of surplus sunitinib tablets will be recorded. If the dose is modified during a medical visit, the patient will return all surplus prior medication.

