6.3.3. Dose Reduction

Titration is not required in patients with grade 1 or 2 treatment-related toxicity. Despite this, investigators should always treat their patients according to their medical judgement and based on individual circumstances.

2 dose-reduction steps are permitted depending on the type and severity of toxicity. If the investigator deems it to be necessary, the reduction of the two dose levels can be performed directly, without needing to wait for a time between both.

Patients requiring more than 2 dose reductions will abandon the treatment phase and enter the follow-up phase.

All adjustments or dose modifications should be clearly documented in the patient's medical record and in the CRF (Investigational product administration).

Once a patient's dose has been reduced, all subsequent cycles will be administered at that same dose, unless a further reduction is required. Dose reescalation will not be permitted as part of the study. Specific cases will be discussed with the study's coordinating investigator [REDACTED]

Table 1. Available dose levels with TH-302 and sunitinib

DOSE LEVEL	TH-302 DOSE	SUNITINIB DOSE
Starting	340 mg/m ² D8, 22	37.5 mg/24h D1-28
-1	280 mg/m ² D8, 22	37.5 mg/24h D1-28
-2	280 mg/m ² D8, 22	37.5 mg/24h D1-22, plus a rest week (3 weeks on / 1 week off)

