6.3.5. Medication Errors or Overdose

Medication errors may be due to a timing error or the drug dosage. These cases should be recorded as an adverse event (AE) or severe adverse event (SAE), as appropriate, in the CRF.

A phase II trial to assess the activity and safety of TH-302 in combination with sunitinib in patients

Should a medication error occur, GETNE must be notified immediately [REDACTED]

Examples of a medication error:

- Medication errors that involve patient exposure to the drug (dispensation/administration of expired medication, dispensation of commercial sunitinib or TH-302 or not allocated for this trial, etc.)
- Medication errors or practices not in accordance with the protocol and that may or may not involve the patient participating in the study (deviations from relevant temperatures, trial medication stock mismatches, etc.).

An SAE will be reported where a patient voluntarily or accidentally ingests more than 60 sunitinib tablets in a single cycle (for example, more than 4 tablets in more than 2 days within a cycle or more than 4 tablets in one day).

An AE will be reported in cases where a patient voluntarily or accidentally ingests 58 or 60 sunitinib tablets in a single cycle. The event will be recorded in the CRF.

Any TH-302 dosage error which leads to > 20% of the expected dose should be considered a TH-302 overdose.

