10.2.3. Intensity Grading of Adverse Events

Adverse events and their severity will be assessed based on *National Cancer Institute Common Terminology Criteria for Adverse Events* (NCI-CTCAE, version 4.0). These criteria can be consulted at the following address:

http://evs.nci.nih.gov/ftp1/CTCAE/CTCAE_4.03_2010-06-14_QuickReference_8.5x11.pdf

10.2.4. Serious Adverse Events (SAEs):

A serious adverse event (SAE) or reaction is any harmful medical event that, regardless of the dose:

- Results in the death of the patient.
- Is life-threatening to the patient or potentially fatal (i.e., the patient is at immediate risk of death at the time of the event).
- Requires patient hospitalisation or the prolongation of existing hospitalisation.
- Results in permanent or significant disability or incapacity.
- Causes a defect, congenital malformation or results in cancer.

In addition, medical and scientific judgement should be used to decide whether other situations should be considered as a serious adverse event, although they do not meet the above criteria, such as those that endanger the patient's life or require intervention to prevent any of the above outcomes.

It must not be confused with the term "severe", which indicates the intensity of the adverse event.

Recording and Reporting of Serious Adverse Events (SAEs):

Information on SAEs, whether related to the treatment or not, will be collected and recorded on the SAE form of the corresponding case report form. SAEs, as defined above, must be recorded from the date the informed consent form was signed, and the pharmacovigilance contact person must be notified immediately, within 24 hours of awareness by the study site, by fax to

Marketing Farmacéutico & Investigación Clínica

The initial report must state the site name and number, the name of the investigator, the patient ID number and initials, patient demographics, study drug administration data and everything known about the serious adverse event, including date of onset, intensity, treatment and relationship to the study drug. If the patient dies, the report should include the cause of death and its potential relationship to the study drug, in addition to the autopsy findings (if available).

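### The sunitinib overdose rule gives two answers for one intake: a 6-capsule day is an SAE by its example and an AE by its cycle count

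*Protocol*

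**What the plan says.** Protocol section 6.3.5 classifies sunitinib overdose by the number of units taken in a cycle. An SAE is to be reported "where a patient voluntarily or accidentally ingests more than 60 sunitinib tablets in a single cycle", and a parenthesis adds "for example, more than 4 tablets in more than 2 days within a cycle or more than 4 tablets in one day". The next sentence makes it an AE when the patient "ingests 58 or 60 sunitinib tablets in a single cycle". The same section has a general rule for all medication errors: each is recorded as an AE or SAE as appropriate, and "Should a medication error occur, GETNE must be notified immediately".

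Section 6.1.1 sets the dose at "37.5 mg per day (1 capsule of 25 mg and 1 capsule of 12.5 mg) orally for 28 days". It also says that a patient who takes an additional dose should omit the dose on the following day. Table 1 in section 6.3.3 keeps the same daily sunitinib dose at level -1 and shortens the dosing period at level -2.

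For an SAE, section 10.2.4 requires that "the pharmacovigilance contact person must be notified immediately, within 24 hours of awareness by the study site".

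**The concern.** The one-day clause is offered as an instance of exceeding 60 in a cycle. A patient on the scheduled 2 capsules a day can exceed 4 in one day and still finish the cycle at or below 60. Some of those totals are exactly the ones that the next sentence calls AEs. Two sites that apply the same paragraph to the same intake could then report it differently.

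At stake is whether the site sends an SAE report within 24 hours or makes an AE entry in the CRF, and whether the event is counted among the SAEs that Protocol section 9.1 and SAP section 1.5.5.1 list as a safety output.

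**Working it through.** **Inputs.** Two capsules a day (section 6.1.1); 28 dosing days per cycle at the starting dose and level -1 (section 5.1 and Table 1); SAE above 60 per cycle, AE at 58 or 60, example of more than 4 in a day (section 6.3.5); next day's dose omitted after an extra dose (section 6.1.1). Section 6.3.5 speaks of tablets, but sunitinib is supplied as capsules; I count one tablet as one capsule.

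**Scheduled total.** 2 × 28 = 56.

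**The plan's figures.** With all other doses taken, one double-dose day gives 27 × 2 + 4 = 58 and two give 26 × 2 + 2 × 4 = 60, so the AE counts fit the regimen. The first example, at its smallest (5 capsules on each of 3 days), gives 25 × 2 + 3 × 5 = 65, which is above 60. If each of those days is followed by an omitted dose, it gives 22 × 2 + 3 × 5 = 59, which is not. The one-day example at its smallest (5 capsules) gives 27 × 2 + 5 = 59. It does not reach the threshold it is meant to illustrate, even with every other dose taken.

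**One high day of k capsules.** With the other 27 days at 2 capsules, the total is 54 + k. With the next day's dose omitted in the same cycle, it is 52 + k.

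| k | 54 + k | class by count | 52 + k | class by count | class by example |
|---|---|---|---|---|---|
| 4 | 58 | AE | 56 | none | not met |
| 5 | 59 | none | 57 | none | SAE |
| 6 | 60 | AE | 58 | AE | SAE |
| 7 | 61 | SAE | 59 | none | SAE |
| 8 | 62 | SAE | 60 | AE | SAE |
| 9 | 63 | SAE | 61 | SAE | SAE |

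Six capsules is a direct contradiction in both columns. Eight is one when the next dose is omitted. Five in both columns, and seven with the omission, is an SAE by the example but falls in no count category. Example and count agree on an SAE from 7 capsules without the omission, and only from 9 with it.

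**Level -2.** Table 1 gives days 1 to 22 but also describes three weeks on treatment and one off, so 22 × 2 = 44 or 21 × 2 = 42 capsules are scheduled. Six in one day totals 21 × 2 + 6 = 48 or 20 × 2 + 6 = 46: an SAE by the example, far below either count. To pass 60 through a single day would take 19 capsules (42 + 19 = 61) or 21 (40 + 21 = 61).

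**The case against.** The strongest reply is that the wording is loose rather than contradictory. The threshold of 60 is exactly 56 + 4. If the examples mean more than 4 surplus units, a one-day surplus of 5 is a 7-capsule day, which totals 61, and the phrase introducing the examples is then correct. This is possible, but the text does not say surplus, and it is not the plain reading. It also fails once the next dose is omitted, because 52 + 7 = 59.

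A reader might instead infer that two separate SAE triggers were intended. No section says so, and this reading alone does not cure the problem: a 6-capsule day would meet the day limit and still fall under the AE sentence.

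A reader might also infer that the ambiguity stops at 6 capsules because 7 exceeds 60. That holds only if every other dose is taken. Under the omission rule of section 6.1.1 the mismatch runs to 8.

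The reply on consequence largely stands. Every medication error is recorded and goes to the sponsor at once. An overdose with serious consequences is an SAE under section 10.2.4 whatever the capsule count, and for other cases that section says "medical and scientific judgement should be used to decide whether other situations should be considered as a serious adverse event". The inference that serious overdoses could go unreported is therefore not supported. What remains open is the label, and the 24-hour route, for a high-intake day without serious consequences.

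**Conclusion.** The rule is internally inconsistent as written. For a 6-capsule day at the starting dose or level -1 it gives both SAE and AE, whether or not the next dose is omitted. The mismatch between example and count covers 5–6 capsules in a day if all other doses are taken, and 5–8 if the next one is omitted. At level -2 the cycle counts have little bearing on the schedule. Nothing else in the Protocol or SAP settles which criterion governs.

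The totals assume one high day, 2 capsules on every other dosing day except any omitted one, and the omitted dose falling in the same cycle.

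This is a minor point. It bears on classification and reporting time for what should be an uncommon event, and on the SAE count to that extent. Sample size, the response-rate analysis and the other efficacy endpoints are unaffected.

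**What to change.** Make the two categories mutually exclusive and delete the parenthetical examples. The conservative form keeps the plan's own one-day limit as a separate trigger:

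> SAE: more than 4 sunitinib capsules in any one day, or more than 60 capsules in a cycle. AE: any other intake above the prescribed schedule, up to 60 capsules in a cycle, with no day above 4 capsules.

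This removes the overlap at 6 and 8 capsules, classifies totals of 57 and 59, and does not depend on whether the next dose was omitted. The sponsor should confirm that the one-day limit is intended, since that is a clinical choice the documents leave open. It should also set a matching cycle limit for level -2, where 42–44 capsules are scheduled and a limit of 60 would allow 16 to 18 surplus capsules (60 − 44 and 60 − 42).

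The cost is two replaced sentences, plus the level -2 limit, at the next amendment, with no change to sample size, visits or analysis. The downside is possibly a few more 24-hour reports for 5–8 capsule days without consequences.

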6.3.6. Concomitant treatment

All concomitant medication, including any drug administered within 4 weeks (28 days) prior to the day 1 visit and 30 days after the last dose of the study drug, must be recorded in the case report form, together with the reason for administration.

The patient should be informed about the importance of consulting the investigator prior to taking additional medications.

Concomitant medication includes any vitamins, herbal remedies, over-the-counter drugs and prescribed medicines.

Any additional treatment that becomes necessary during the study, and any change to concomitant drugs, must be recorded in the corresponding section of the case report form, including the name, dose, duration and indication of each drug.

Should medication be administered intermittently, or in relation to an adverse event, this adverse event should be recorded on the adverse event form of the case report form.

- **Disallowed concomitant treatment:**
 - Other oncology drugs (chemotherapy, immunotherapy, targeted therapy) during the treatment phase, whether approved healthcare drugs or under clinical trial.
 - Drugs that are known to cause QT interval prolongation, given the risk of developing polymorphic ventricular tachycardia. (Annex 4)
 - Strong or moderate CYP3A4 inhibitors

If, during the study, a patient requires treatment with one of these drugs for a limited period of time, TH-302 and sunitinib will not be administered simultaneously. Treatment will be reviewed together with the medical monitor, who will supply the dosage rules based on the half-life of the medicinal products, TH-302 and sunitinib, in addition to other clinical considerations. The medical monitor will advise the investigator, who will assess the search for alternative medicines.

- **Concomitant treatment not recommended:**

- Chronic immunosuppressant treatment, including systemic corticosteroids. Short courses of topical/inhaled or systemic corticosteroids are permitted
- Herbal products

For up-to-date information on drug interactions (substrates, inhibitors or inducers), visit the following website:

<http://www.fda.gov/Drugs/DevelopmentApprovalProcess/DevelopmentResources/DrugInteractionsLabeling/ucm093664.htm#classSub>

- **Permitted concomitant treatment**

- Treatment with somatostatin analogues (octreotide LAR or lanreotide Autogel) at doses established in the summary of product characteristics and with the aim of controlling the symptoms of the patient's underlying disease
- Any treatment for pre-existing comorbidities, complications or symptomatic control, taking into account the precautions mentioned above, and recorded in the patient's medical record and in the CRF.
- Stimulation of colony formation, following standard treatment and institutional guidelines. Its use is not allowed as primary prophylaxis, but is allowed as secondary treatment or prophylaxis, in the event that the alternatives of dose reduction or treatment delay are not deemed appropriate.
- Transfusion of red blood cells/platelets or erythropoietin for supportive treatment of anaemia or for the prompt treatment of thrombopenia, following standard treatment and institutional guidelines.
- Hormone replacement therapy within 2 months prior to study enrolment shall not constitute an exclusion criterion. The same dose must be maintained throughout the course of the study.
- Palliative radiotherapy of non-target lesions is permitted, if necessary, while taking part in the study. The location, total dose received and treatment dates should be recorded in the case report form.

7. PATIENT SELECTION

7.1. Inclusion Criteria

1. Age \geq 18 years capable of giving informed consent.
2. ECOG performance status (Eastern Cooperative Oncology Group) 0 or 1
3. Pancreatic neuroendocrine tumours (pNET) diagnosed histologically with a Ki67 \leq 20% (well- or moderately-differentiated tumours).
4. Evidence of unresectable or metastatic disease. Locally advanced disease must not be amendable to surgical resection or radiation therapy with curative intent.
5. Prior systemic therapy is not permitted. Patients may be treated with somatostatin analogues prior to or during the trial. Concomitant or prior interferon (IFN) treatment is not permitted.
6. Tumour progression documented by CT scan, MRI or octreoscan within 12 months prior to the baseline visit.
7. Measurable disease by RECIST 1.1 criteria. Measurable lesions that have been previously radiated will not be considered target lesions unless increase in size has been observed following completion of radiation therapy.
8. The patient must be able to consume the medication orally.
9. Life expectancy more than 12 weeks.
10. The required laboratory values corresponding to adequate organ function and bone marrow are as follows.
 - Aspartate aminotransferase (AST) and alanine aminotransferase (ALT) \leq 2.5 x upper limit of normal (ULN), or AST and ALT \leq 5 x ULN if liver function abnormalities are secondary to underlying malignancy.
 - Total serum bilirubin \leq 1.5 \times ULN
 - Serum albumin \geq 3.0 g/dl
 - Absolute neutrophil count \geq 1500/ μ l.
 - Platelets \geq 100,000/ μ l
 - Haemoglobin \geq 5.6 mmol/l (9 g/dl)
 - Creatinine clearance $>$ 40 ml/min (Cockcroft and Gault Formula)
11. Suitable cardiac function:
 - 12-lead ECG with no pathological findings (non-clinically significant abnormalities are permitted)
 - Normal echocardiogram/MUGA normal (LVEF \geq 50%)
12. Informed consent with date and signature indicating that the patient (or legal representative) has been informed of all study aspects prior to enrolment.
13. The patient must be able to comply with the required study visits, treatment, laboratory tests and other study procedures.

7.2. Exclusion Criteria

Patients must NOT meet any of the following exclusion criteria:

1. Previous treatments with chemotherapy, anti-VEGF monoclonal antibodies, tyrosine kinase inhibitors (TKI), mTOR inhibitors or interferon (IFN) administered for advanced disease.
2. Prior treatment with another hypoxia-activated drug under clinical trial.
3. Major surgery, radiotherapy or systemic therapy within 4 weeks prior to study enrolment, except palliative radiotherapy for non-target metastatic lesions.
4. Prior high-dose chemotherapy requiring haematopoietic stem cell rescue.
5. Immunosuppressive drugs such as cyclosporine, tacrolimus, azathioprine, or long-term corticosteroids taken concurrently or within 3 months prior to study enrolment.
6. Treatment, within 7 days prior to study enrolment, with known strong CYP3A4 inhibitors or inducers, or drugs that prolong the QT interval.
7. Prior radiation therapy to > 25% of the bone marrow.
8. Treatment within another clinical trial.
9. Uncontrolled brain metastatic disease, spinal cord compression, carcinomatous meningitis or leptomeningeal disease. Patients should have completed surgery or radiation therapy for existing brain lesions, should not have documented increase in size of said lesions over the three months prior to the first study treatment dose, and should be asymptomatic.
10. Diagnosis of any second malignancy within the last 3 years, except for adequately treated basal cell or squamous cell skin cancer, or carcinoma in situ of the cervix.
11. Clinically significant cardio/cerebrovascular disease within 12 months prior to treatment initiation, including:
 - Myocardial infarction
 - Severe/unstable angina
 - Coronary/peripheral artery bypass graft
 - Congestive heart failure NYHA (New York Heart Association) Class III or IV, or patients with a history of congestive heart failure NYHA class III or IV, unless an echocardiogram or MUGA scan within 3 months prior to screening shows a left ventricular ejection fraction \geq 45%.
 - Significant cardiac valvular heart disease.
 - Cerebrovascular accident including transient ischaemic attack.
 - Pulmonary thromboembolism.
12. Cardiac arrhythmias (NCI CTCAE version 4.0 grade \geq 2), atrial fibrillation of any grade, or QTc interval > 450 msec for males or > 470 msec for females.
13. Hypertension that cannot be controlled despite optimal medical therapy (> 150/100 mmHg)
14. Chronic obstructive pulmonary disease (COPD) or any lung disease accompanied by hypoxaemia or oxygen saturation < 90% after a 2-minute walk.
15. Current treatment with therapeutic doses of acenocoumarol (administration of low doses of acenocoumarol up to 2 mg/24 h for deep vein thrombosis prophylaxis is permitted).
16. Known human immunodeficiency virus (HIV) infection.

17. Pregnant or breast-feeding. All female patients of childbearing age must have a negative pregnancy test (blood or urine) prior to study enrolment.
18. Prior allergic reaction to ingredients structurally similar to TH-302 or sunitinib or to any of the drugs' excipients.
19. Non-healing wound, fistulae, active stomach ulcer or bone fractures.
20. Any condition (medical or psychiatric) or reason that, in the opinion of the investigator, would interfere with the patient's ability to participate in the clinical trial, by placing the patient at excessive risk or by complicating the interpretation of the safety data, therefore being unsuitable for enrolment in the study.

